4.3.5. Safety Analysis Set

The Safety analysis set includes all randomized participants who received at least 1 dose of study intervention. Participants will be analyzed according to the intervention they actually received. Randomized participants for whom it is unclear whether the study medication was taken will be included in the safety analysis set as randomized. For participants receiving more than one IMP during the study (i.e., placebo and dupilumab), the actual study intervention group for as treated analysis will be the dupilumab group.

4.4. Reporting Conventions

Statistical analysis will be performed using SAS® Version 9.4 or higher.

Standardized and validated SAS macros from PPD will be used to set-up table, listing, figure (TLF) formats (headers/footers and tabulation format) and tabulate the summaries. All tables and listings will be independently validated using double programming; all figures will be independently validated manually.

4.4.1. Study Intervention labels

The following study intervention labels will be used in the Tables, Figures and Listings:

Table 4-1 Study Intervention labels

Study Intervention order	Study Intervention group	Study Intervention Label
1	Placebo	Placebo
2	Dupilumab 200 mg q2w	Dupilumab 200 mg q2w
3	Total	Total

4.4.2. Visit naming Conventions

The electronic Case Report Form (eCRF) visit label will be used to classify the assessments. Where applicable, visit name will be formatted as “Week X” in summaries.

4.4.3. Visit Windows

The visit windows as defined in [Section 15.5](#) will be applied to all endpoints.

4.4.4. Unscheduled Visits

Unscheduled visit measurements will be used in the analysis on efficacy variables and will be included in the by-visit summaries for the safety variables if they are re-allocated to scheduled visits according to the visit window definitions in [section 15.5](#).

4.4.5. Display of Data Summary and Analysis

Continuous variables will be summarized using descriptive statistics, including the following: sample size (n), mean, standard deviation (SD), median, first quartile (Q1), third quartile (Q3), minimum and maximum for each study intervention group.

All mean, Q1, Q3 and median values will be formatted to one more decimal place than the measured value. SD values will be formatted to two more decimal places than the measured value. Minimum and maximum will be formatted to the same number of decimal places as the measured value.

95% confidence intervals (CIs) will be two-sided and displayed to the same level of precision as the statistic they relate to. If an estimate or a CI is not estimable, it will be presented as ‘NE’. If neither an estimate, nor its CI are estimable, it will be presented as simply ‘NE’, not displaying ‘NE’ twice.

The p-values will be two-sided and will be rounded to three decimal places. If a p-value is less than 0.001 it will be reported as ‘<0.001’.

Categorical and ordinal data will be summarized using the counts and percentages. When count data are presented, the percent will be suppressed when the count is zero in order to draw attention to the non-zero counts. A row denoted ‘Missing’ will be included in count tabulations for demographics, baseline characteristics and compliance to account for missing values. No percentages will be displayed on the ‘Missing’ rows and the percentages on the other rows will be based on the number of non-missing observations. Unless otherwise specified, the denominator for all other percentages will be the number of participants in that study intervention within the specific analysis set of interest. All percentages will be rounded to one decimal place. The number and percentage of responses will be presented in the form xx (xx.x), where the percentage is in the parentheses. When the numerator is equal to the denominator, the percentage should be presented as (100) instead of (100.0), unless otherwise specified.

All listings will be sorted for presentation in order of assigned study intervention arm, study center number, participant number and date of procedure or event.

4.4.6. Baseline, study day and duration derivations

For assessments to be completed daily during the week prior to baseline visit (i.e., asthma sleep disturbance questionnaire, actigraphy parameters, sleep diary, ADSD and ANSD), the baseline value will be calculated by averaging the data collected/recorded from Day -6 to Day 1 (for ADSD: from Day -7 to Day -1). For actigraphy parameters, assessments performed at the same date as Day 1 will be taken into account for baseline calculation only if the end time of assessment is before 12 pm, reflecting the last night before the visit.

If less than 4 measurements are available between Day -6 and Day 1 (for ADSD: between Day -7 and Day -1), the most recent 4 measurements will be used for the calculation; if finally, less than 4 measurements are available, it will be considered as missing.

For all the other parameters, the baseline value is generally defined as the last available valid (non-missing) value up to and including the day of first dose of IMP. For participants randomized but not treated, the baseline value is defined as the last available value up to and including the day of randomization.

If multiple valid values of a variable (efficacy or safety) exist within a same day (and the recorded times of measurement do not enable to identify which of them is the last assessment), the value measured during the scheduled visit will be used as Baseline in the analysis. If none of those values were assessed during a scheduled visit, then all these measurements will be used for the analysis and the average will be calculated to derive the baseline value.

Baseline safety and efficacy results are presented in the safety and efficacy analyses.

The reference day (denoted as Day 1) for the calculation of extent of exposure and study day for AE listings will be the day of the first administration of IMP:

- Extent of exposure (see [Section 7.2.1](#))
- Study day for AE listing: AE onset date – first administration date of IMP + 1

The reference day (denoted as Day 1) for the calculation of study day of efficacy assessments will also be the day of the first administration of IMP (except for participants randomized but not exposed).

- For visit prior to the first administration of IMP, study day = assessment date – the first administration of IMP.
- For visit at or after the first administration of IMP, study day = assessment date – the first administration of IMP + 1.

Note: For participants randomized but not treated, the reference day will be the randomization date.

Intervals that are listed and/or tabulated in weeks will be transformed from days to weeks by using (without rounding) the following conversion formula:

$$\text{WEEKS} = \text{DAYS} / 7$$

Intervals that are listed and/or tabulated in months will be transformed from days to months by using (without rounding) the following conversion formula:

$$\text{MONTHS} = \text{DAYS} / 30.4375$$

The last on-treatment value of safety parameters is the final measurement assessed during the treatment-emergent adverse event period regardless of the introduction of rescue therapy and including measurements at unscheduled visits.

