**Number of participants:**

Approximately 260 participants will be randomly assigned to study intervention, respectively in a 1:1 ratio for dupilumab: placebo (approximately 130 participants to dupilumab group and 130 to placebo group) to achieve 234 evaluable participants (with expected 10% dropout rate) for an estimated total of 117 evaluable participants per intervention group. Randomization will be stratified according to 5 strata: one stratum for all participants included in the [REDACTED] (regardless of dose level of inhaled corticosteroid [ICS], regardless of region) and 4 strata for participants not included in [REDACTED], according to region and ICS dose (Eastern Europe with high ICS dose, Eastern Europe with medium ICS dose, rest of world [ROW] with high ICS dose, and ROW with medium ICS dose). In total, no less than 40% participants need to be in "high ICS" strata, and no more than 25% participants need to be in "Eastern Europe" strata.

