## 4 STUDY DESIGN

### 4.1 OVERALL DESIGN

This is a Phase 4, randomized 1:1, multicenter study with a 12-week double-blind, parallel-group, placebo-controlled treatment period to assess the effect of dupilumab in improving sleep outcomes, asthma control, and health-related quality of life, and in reducing daytime and nighttime asthma symptoms.

Study duration for each participant will be approximately 16 weeks and up to 29 weeks.

The study includes 3 study periods:

- Screening period:
  - Screening Period 1: Day -35 to Day -12, from signed informed consent.
  - Screening Period 2 (Pre-baseline assessments): participants eligible to continue will complete the assessments specified in the SoA from Day -11 to Day -1 (right before Day 1).
  - If preferred by the participant and the investigator for logistic reasons, screening visit 1 (SV1) and screening visit 2 (SV2) can be merged into a single on-site visit.  
Importantly, this single screening visit will have to be done on Day -11 at the latest.
- Randomized, placebo-controlled treatment period: 12 weeks from baseline (Day 1).
- Post treatment follow-up period: up to 12 weeks or until the participant switches to commercialized dupilumab (or other biologic product), whichever comes first.

Participants who fulfill the inclusion criteria and do not meet any of the exclusion criteria will be randomized centrally (1:1) to one of the following IMPs:

- Dupilumab: participants will receive a loading dose of 400 mg of dupilumab (two 200 mg dupilumab SC injections) on Day 1, followed by one 200 mg dupilumab SC injection Q2W for 12 weeks.
- Placebo: participants will receive two placebo matching dupilumab 200 mg SC injections on Day 1, followed by one of placebo matching dupilumab 200 mg SC injection Q2W for 12 weeks.

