#### NOTES:

- Historical values of blood eosinophil count meeting the eligibility criterion measured within 6 months prior to SV1 in the absence of OCS treatment are allowed.
- FeNO value to be checked for eligibility at V2 as well.

I 05. ACQ-5  $\geq 2.5$  at SV1 and Visit 2, prior to randomization.

I 06. Pre-BD FEV1  $\leq 80\%$  of predicted normal during screening and at V2, prior to randomization.

I 07. Exhibit bronchodilator reversibility ( $\geq 12\%$  and 200 mL improvement in FEV1 post SABA administration) during screening period, prior to randomization, unless reversibility test meeting the inclusion criteria was done within 6 months prior to SV1.

I 08. Weekly average nocturnal awakenings due to asthma symptoms in the week prior to SV1 is  $\geq 1$ .

I 09. Willing and able to comply with all clinic visits and study-related procedures.

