### 9.2 SAMPLE SIZE DETERMINATION

The sample size was chosen to enable an adequate characterization of the efficacy between dupilumab 200 mg Q2W and placebo with regards to the primary endpoint, change from baseline in sleep disturbance score at Week 12.

The sample size calculation was based on the subset of adult participants who had more than 1 weekly average nocturnal awakening at baseline, baseline ACQ-5  $\geq 2.5$ , EOS  $\geq 150$  cells / $\mu$ L and FeNO  $\geq 25$  ppb in the previous [REDACTED] evaluating efficacy of dupilumab for participants with moderate-to-severe asthma.

The observed treatment difference on mean sleep disturbance score of the dupilumab group with 200 mg Q2W dosing in [REDACTED] versus placebo at Week 12 was [REDACTED]. A conservative estimate was used that assumes the treatment difference to be [REDACTED] at Week 12. Assuming normal distribution of the change in sleep disturbance score, a common standard deviation (SD) of [REDACTED], which came from the observed data in [REDACTED], with 117 participants per group, the study will have 90% power to detect an effect size of [REDACTED] using a two-sided test with alpha=0.05 for change from baseline in sleep disturbance score at Week 12 in the dupilumab 200 mg Q2W group versus placebo.

Assuming a 10% dropout rate, approximately 260 participants will be randomly assigned to study intervention to achieve 234 evaluable participants for an estimated total of 117 evaluable participants per intervention group.

In order to mitigate the risk of potential different responses based on the Sleep Disturbance Questionnaire before and after amendment 01, the primary analysis of change from baseline in sleep disturbance score will exclude the participants who use the original questionnaire at baseline. The number of participants randomized up to the implementation of this protocol amendment is limited (ie,  $\leq 10$ ), therefore the study power can be preserved at  $\geq 89\%$  and therefore no participant replacement is planned.

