All efficacy analyses will be performed on the ITT analysis set, except for that of the primary efficacy endpoint, which will employ the ITTp set.

Participant will be analyzed for efficacy according to the study intervention group to which they are allocated by the IVRS according to the randomization schedule at the randomization visit (as randomized), irrespective of the study intervention actually received.

For the analysis of primary objective in the treatment period,

- The null statistical hypothesis tested is that there is no mean treatment difference between Dupilumab and placebo on sleep disturbance score in adult participants moderate-to-severe uncontrolled asthma and evidence of Type 2 inflammation.
- The alternative statistical hypothesis tested is that there is a mean treatment difference between Dupilumab and placebo on sleep disturbance score in adult participants moderate-to-severe uncontrolled asthma and evidence of Type 2 inflammation

Note that due to the small sample size of the [REDACTED], no statistical testing will be conducted for analyses in the [REDACTED] analysis set. Summary statistics with 95% CI by study intervention group will be provided.

All efficacy measurements collected during the study will be considered for analyses, including those obtained after IMP discontinuation, except if study intervention discontinuation was due to the COVID-19 pandemic; for more details, refer to [Table 2-2](#).

For efficacy endpoints where a change from baseline is assessed, only the participants who have a baseline and at least one post-baseline value available will be included in the analysis (number of participants included in the analysis model reported in the table).

All daily assessments (i.e., asthma sleep disturbance questionnaire, sleep diary) will be analyzed as monthly averages, calculated from the 28 days immediately preceding (and including) the theoretical expected day of the study visit calculated from the day of first IMP intake (note that 28 days is a maximum and that it could be less, in case fewer assessments have been performed within the corresponding 28 days window).

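### No check before randomization confirms that a participant has the 4 run-in questionnaire entries needed for a primary baseline

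*SAP*

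**What the plan says.** - **Run-in.** Protocol 4.1 has eligible participants complete the scheduled assessments from Day -11 to Day -1. A merged screening visit must take place by Day -11 at the latest. The questionnaire is completed once a day on waking (Protocol 8.1.5).
- **Baseline rule.** SAP 4.4.6 averages the entries from Day -6 to Day 1. If fewer than 4 exist in that week, the most recent 4 are used; "if finally, less than 4 measurements are available, it will be considered as missing".
- **Entry to the model.** SAP Section 8 states that, for change-from-baseline endpoints, "only the participants who have a baseline and at least one post-baseline value available will be included in the analysis". The baseline score is also a covariate (SAP 8.1.1), and SAP 8.1.3 makes no imputation in the primary analysis.
- **Analysis set.** ITTp (SAP 4.3.3) removes only users of the original questionnaire. It does not remove participants without a baseline.
- **Eligibility.** Criteria I 01 to I 11 and E 01 to E 32 contain no diary count. The nearest are I 09, "Willing and able to comply with all clinic visits and study-related procedures", and E 29, which leaves the risk of noncompliance to the investigator's judgement. Protocol Section 8 requires screening evaluations to be completed and reviewed, but for the purpose of confirming the eligibility criteria. By contrast, ACQ-5, FeNO and pre-bronchodilator FEV1 must all qualify again at Visit 2.

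**The concern.** The plan protects the length of the run-in but not its content. The instrument behind the primary endpoint has no numerical condition at Visit 2, while three other measures do. A participant with 0 to 3 entries meets every countable criterion, can be randomized and can receive 12 weeks of blinded injections, yet can never enter the primary comparison. The number of entries is visible in the e-diary on the day of randomization, and a pre-treatment baseline cannot be collected once dosing has started.

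At stake are some precision, a departure from analysing everyone randomized for an avoidable reason, and participation that does not serve the primary question. The 10% allowance in Protocol 9.2 is labelled dropout and makes no mention of missing baselines. The same baseline rule applies to the Sleep Diary, which supplies nocturnal awakenings, the second step of the testing hierarchy (SAP 8.2.13).

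**Working it through.** **Inputs from the documents.** Two-sided alpha 0.05; 1:1 allocation; 10% dropout; 260 randomized; 234 evaluable. Protocol 9.2 says that "with 117 participants per group, the study will have 90% power to detect an effect size of" a value that is blacked out. Up to 10 participants are excluded for the original questionnaire, with stated power of at least 89%.

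**Assumptions.** Daily completion rate, within-person correlation and the resulting missing-baseline rate; the documents give none of these. I read the fallback to the most recent 4 entries as reaching over the whole run-in, which gives 11 entries, or 12 if both Day -11 and Day 1 count.

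**1. Reproduce the plan's figures.**
- 117 / 0.9 = 130 per arm, so 260 randomized; 260 × 0.9 = 234. This agrees.
- With the effect size redacted, the standardized effect is solved back: d = (1.960 + 1.2816) × √(2/117) = 0.424.
- Power = Φ(d × √(n/2) − 1.960), with n per arm. With the 10 exclusions, (260 − 10) × 0.9 = 225 evaluable, n = 112.5, and power = Φ(3.179 − 1.960) = 88.9%, in line with the stated figure. Taking 234 − 10 = 224 gives 88.7%.

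**2. How often would fewer than 4 entries occur?** With independent days, P(X ≤ 3) for X ~ Binomial(days, p):

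| Daily completion | 11 days | Expected of 260 | 12 days |
|---|---|---|---|
| 80% | 0.02% | 0.1 | 0.01% |
| 70% | 0.4% | 1.1 | 0.2% |
| 60% | 2.9% | 7.6 | 1.5% |
| 50% | 11.3% | 29 | 7.3% |

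The fallback matters: with the 7-day window alone, the 80% row would be 3.3% and the 70% row 12.6%.

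Independence is favourable to the plan, because non-use tends to cluster (an unused device, a disengaged participant). A beta-binomial over 11 days with an assumed within-person correlation of 0.1 to 0.3 gives 0.2% to 2.2% at 90% completion, 1.1% to 6.2% at 80%, and 3.9% to 12.4% at 70%.

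**3. Effect on power.** Evaluable N = randomized × (1 − m) × 0.9, where m is the assumed missing-baseline rate:

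| m | Power from 260 | Power from 250 (after 10 exclusions) |
|---|---|---|
| 0% | 90.0% | 88.9% |
| 1% | 89.7% | 88.5% |
| 2% | 89.4% | 88.2% |
| 3% | 89.1% | 87.9% |
| 5% | 88.5% | 87.3% |

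The cost from 260 is 90.0 − 89.7 = 0.3 points at 1% and 90.0 − 88.5 = 1.5 points at 5%. Keeping 234 evaluable would need 234 / (0.99 × 0.9) = 263 randomized at 1% and 234 / (0.95 × 0.9) = 274 at 5%.

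**The case against.** The best counter-argument is that the event is rare and already controlled. The fallback means that a participant is lost only with 0 to 3 of about 11 or 12 entries. Protocol Section 8 makes adherence to the schedule required and bars waivers, and E 29 lets the investigator exclude someone who has missed most of the run-in. SAP 8.1.7, discussing Covid-19, does not expect participant-reported data to be missing. Interim re-estimation can raise the sample to 520, and the MMRM uses the available visits of participants who drop out, so the power figures are somewhat pessimistic.

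Most of this stands, and it limits the size of the point. It does not close the gap. These are general duties and judgements; none ties randomization to the SAP's threshold of 4.

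A reader might go further in four ways that the documents do not support.
- **That this pushes power below the stated 89%.** With no missing baselines at all, the 10 questionnaire exclusions already bring power to about 88.7% to 88.9%. The shortfall against 89% is not caused by this issue.
- **That the SAP addendum shows primary diary data to be missing.** Items 1 and 2 report duplicate records and illogical Sleep Diary answers. Neither reports absent questionnaire entries.
- **That the treatment comparison is biased.** The missingness arises before blinded dosing, so it should not differ by arm.
- **That ITTp excludes these people.** The set keeps them; the model loses them.

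Two limits remain. The home-diary rows of the protocol's own schedule are not legible in the copy reviewed; the SAP's copy (15.2), from a SAP based on amendment 01, shows no minimum count. At the Metasite, entries continue until dosing, up to 5 days after randomization (Protocol 10.7), so a low count at randomization there need not mean a missing baseline.

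**Conclusion.** The point holds as a modest gap in design. The baseline rule, the model-entry rule and the absence of imputation together remove a randomized participant with fewer than 4 run-in entries from the primary model, and nothing in the eligibility criteria or at Visit 2 checks for this.

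The size rests on an unstated completion rate. It is negligible if daily completion is about 80% and independent between days, about 3% at 60% (1.5% with 12 days), and higher with clustering. For 1% to 5% missing, the cost is about 0.3 to 1.5 points of power. These figures use a standardized effect solved back from the plan's own 117 per group and 90% power. The consequence is lost precision and avoidable non-contribution to the primary analysis, so this is a cheap improvement and not a threat to validity.

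**What to change.** Add one line to Protocol 5.1 or to the Visit 2 note in the schedule of activities. Before the IVRS/IWRS call, the site confirms in the e-diary:
- at least 4 Asthma Sleep Disturbance Questionnaire entries in the run-in, matching SAP 4.4.6;
- at least 4 Sleep Diary entries that pass the logic checks in SAP addendum item 2, since a day that fails any of them is not used and a plain count would not secure the nocturnal awakenings baseline.

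If either is not met, defer Visit 2 within the existing screening period until it is. At the Metasite, let the check take account of entries that continue up to first dosing.

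If enrolment has closed, report by arm how many randomized participants had no baseline. Also state whether the multiple imputation in SAP 8.1.5, which lists the baseline score but is silent on this, imputes a missing one.

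Cost: a few delayed randomizations or extra screen failures. No new assessment is needed, because the entries are already captured electronically.

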The Investigator or delegate will train the participant (or caregiver) how to prepare and inject IMP at Visit 2. The site staff will inject the first dose of the two injections. The participant (or caregiver) will perform the second injection under the supervision of the Investigator or delegate. This training must be documented in the participant's study file. At subsequent administrations, participants are allowed to self-inject IMP at home.

For participants enrolled through Science37 Metasite, IMP will be administered by a mobile study nurse at the randomization dosing visit. As described above, the participants/caregivers will be instructed how to prepare and self-inject/inject the IMP at the first dosing visit and will be allowed to self-administer/administer for the remainder of the treatment period. If the participant is not comfortable with self-administration, the mobile study nurse will perform the administrations at home visits at every 2 weeks, according to the scheduled IMP administrations. The mobile study nursing management with all related activities will be under the responsibility of Science37.

Participants should be instructed to avoid missing any dose of medication during the study. Any participant who misses one dose should be reminded to be diligent, in order to avoid further missing doses thereafter. In case of missed dose(s), no loading dose of two injections will be administered when restarting the treatment, whatever the number of missed doses. The participants should continue their scheduled IMP treatment and visits, even if more than two consecutive doses were missed.

When the participant has a study visit, the IMP will be administered following clinical procedures and blood collection. Participants should be monitored for at least 30 minutes. The monitoring period may be extended as per country-specific or local site-specific requirements.

If the participant (or caregiver) is unable or unwilling to administer IMP, injections can be performed at the site by way of unscheduled visits; or arrangements can be made for qualified site personnel and/or health care professionals (eg, visiting nurse service) to administer IMP for the doses that are not scheduled to be given at the study site or if the participant can't attend the on-site visit.

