#### 9.4.1 General considerations

The multiplicity procedure is proposed to control the overall Type I error rate for testing the primary and selected secondary endpoints assessed for dupilumab 200 mg Q2W versus placebo. The overall alpha is 0.05. The list of secondary endpoints to be tested in the hierarchical order will be specified in the SAP.

The baseline value is defined generally as the last available value before randomization.

The primary analysis will be performed on the ITTp population, and all other efficacy analyses will be performed on the ITT population, unless otherwise noted. All safety analyses will be performed on the Safety Population.

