9.3. Vital Sign Measurements

Vital signs including weight, heart rate (HR), sitting systolic (SBP) and diastolic blood pressure (DBP), temperature and respiration rate, will be collected at screening visit, at baseline visit (Day 1) before receiving the IMP and then at all subsequent visits.

The vital sign results will be summarized for the safety analysis set by study intervention group using descriptive statistics and for each visit or study assessment (baseline, each-post-baseline time point, last on-treatment value).

The Potentially Clinically Significant Abnormalities (PCSA) at any time during the TEAE period will be summarized for the safety analysis set by study intervention group, using number and percentage. The PCSA are provided in [Section 15.7](#).

All measurements collected during the TEAE period, including values from unscheduled visits, will be considered for the PCSA summaries. The summaries will include participants in the safety analysis set who have at least 1 assessment performed during the TEAE period.

A listing of participants with at least 1 post-baseline PCSA will be provided and will display the participants' profile over time of all vital sign parameters.

Individual data listings will include the following flags:

- Baseline values will be flagged "B",
- Parameter values reaching a PCSA limit will be flagged (+, or - depending on the direction).

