15.7. Potentially Clinically Significant Abnormalities (PCSA) Criteria

Table 15-3 Potentially Clinically Significant Abnormalities Criteria

CRITERIA for POTENTIALLY CLINICALLY SIGNIFICANT ABNORMALITIES

(From BTD-009536 May 21, 2014)

Parameter	PCSA	Comments
HR	≤ 50 bpm and decrease from baseline ≥ 20 bpm	To be applied for all positions (including missing) except STANDING.
	≥ 120 bpm and increase from baseline ≥ 20 bpm	
SBP	≤ 95 mmHg and decrease from baseline ≥ 20 mmHg	To be applied for all positions (including missing) except STANDING.
	≥ 160 mmHg and increase from baseline ≥ 20 mmHg	
DBP	≤ 45 mmHg and decrease from baseline ≥ 10 mmHg	To be applied for all positions (including missing) except STANDING.
	≥ 110 mmHg and increase from baseline ≥ 10 mmHg	
Weight	$\geq 5\%$ increase from baseline $\geq 5\%$ decrease from baseline	FDA Feb 2007

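### SAP 4.4.6 sets baseline by calendar day with no pre-dose condition and is not reconciled with Addendum #7 or Protocol 9.4.1, so an off-schedule Day 1 post-injection vital sign can drop out of the PCSA summary

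*SAP*

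**What the plan says.** - **SAP 4.4.6.** For parameters that are not averaged over the pre-baseline week, "the baseline value is generally defined as the last available valid (non-missing) value up to and including the day of first dose of IMP". Where several values fall on one day and their recorded times do not show which came last, "the value measured during the scheduled visit will be used as Baseline in the analysis". By implication, where the times do show it, the last one is taken. The section sets a clock limit for actigraphy alone: a Day 1 assessment counts "only if the end time of assessment is before 12 pm".
- **Protocol 9.4.1.** "The baseline value is defined generally as the last available value before randomization".
- **SAP Addendum #7.** If a participant has several records on one date, the analysis uses the earliest by recorded time. The item cites no SAP section and mentions neither baseline nor PCSA.
- **SAP 9.3.** Vital signs are collected "at baseline visit (Day 1) before receiving the IMP and then at all subsequent visits". For the abnormality tables, "All measurements collected during the TEAE period, including values from unscheduled visits, will be considered for the PCSA summaries". Under SAP Section 9 that period opens with the first administration.
- **SAP 15.7.** Each heart rate, systolic and diastolic criterion joins a threshold to a change from baseline, for example "≥ 120 bpm and increase from baseline ≥ 20 bpm".
- **Protocol 6.1.** At a study visit the injection comes after the examinations and blood draw. Afterwards, "Participants should be monitored for at least 30 minutes"; no vital-sign measurement is specified for that interval.
- **SAP Section 13.** Three changes from the protocol are listed: averaging of nocturnal awakenings, COVID-19 discontinuations, and the safety set. The baseline definition is not among them.

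**The concern.** A baseline should precede the exposure whose effect is measured against it. The 4.4.6 rule works by calendar day, so a value recorded on the dosing day after the injection qualifies. SAP 9.3 treats the same value as on-treatment. One reading can therefore be both the reference and the observation.

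An extra reading on Day 1 is most plausible in someone who becomes unwell during the observation period. Because the criteria in SAP 15.7 need a change from baseline, a reading used as its own baseline can never qualify. Protocol 2.3.1 names systemic hypersensitivity as an important identified risk, and clinically significant vital-sign changes sit within a secondary safety endpoint. The abnormality table should show a first-dose reading of this kind if one is recorded.

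**Working it through.** No stated sample size, power or alpha depends on this rule, so there is no plan figure to reproduce. The check applies each baseline rule to the SAP 15.7 criteria. The readings below are assumed, because the documents give none.

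**Criteria (SAP 15.7).** Low systolic pressure: value ≤ 95 mmHg and decrease from baseline ≥ 20 mmHg. High heart rate: value ≥ 120 bpm and increase from baseline ≥ 20 bpm.

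**Case 1: a pre-dose and a later unscheduled post-dose reading on Day 1.** Assume systolic 124 before and 92 after the injection.

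| Rule | Baseline | Change for the 92 reading | Counted as PCSA? |
|---|---|---|---|
| 4.4.6, times recorded | 92 | 92 − 92 = 0 | No |
| 4.4.6, times do not settle the order | 124 | 92 − 124 = −32 | Yes |
| Addendum #7 applied to all records | 124 | reading discarded | No |
| Addendum #7 for baseline only, SAP 9.3 for PCSA | 124 | −32 | Yes |
| Explicit pre-dose baseline | 124 | −32 | Yes |

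Post-dose values of 90 and 95 behave the same way: changes of −34 and −29 from 124, but 0 when the value is its own baseline. Heart rate is alike. With 78 before and 128 after, 128 − 78 = +50 meets the criterion and 128 − 128 = 0 does not. A later reading can also be masked under 4.4.6: a Week 4 heart rate of 122 is 122 − 78 = +44 (criterion met) against the pre-dose value, but 122 − 128 = −6 (not met) against the post-dose one.

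**Case 2: no pre-dose reading on Day 1.** Assume screening 125 and a single Day 1 reading of 92 after the injection. Under 4.4.6 the baseline is 92, the change is 0, and nothing is counted. Addendum #7 does not help, because there is only one record on that date. With a pre-dose baseline of 125 the change is 92 − 125 = −33, and it is counted.

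**Case 3: Day 1 as planned.** Only the scheduled pre-dose reading exists, so there is nothing to misassign.

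**Consistency with other SAP rules.** The post-baseline windows in SAP 15.5 open on Day 2 or later, and SAP 4.4.4 admits unscheduled safety values to by-visit summaries only if they fall in a window. In those summaries a Day 1 post-dose value has no place except as baseline.

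**Protocol against SAP.** In Case 2 the Protocol 9.4.1 rule would select the screening value. At the Metasite, where the loading dose may follow randomization by up to 5 days, a value recorded in between is eligible under the SAP rule and not under the protocol rule. The two definitions are therefore not interchangeable.

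**The case against.** The strongest reply has four parts.

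**The triggering data are not planned.** Day 1 vital signs and spirometry precede the injection, and no post-dose reading is scheduled. This stands. A reader might infer from 4.4.6 that a post-injection reading ordinarily becomes the baseline; the documents do not support that. The exposure is confined to Cases 1 and 2.

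**Addendum #7 is later than 4.4.6 and points to the earliest record.** This stands in part. Nothing limits #7 to the daily questionnaires, and Addendum #1 already gives those their own duplicate rule, so it is not safe to assume that #7 leaves vital signs alone. But #7 cures one fault by creating another. Taken literally it removes the later reading that SAP 9.3 says must be considered, and it is silent on Case 2. Case 1 comes out right under #7 only if it governs baseline while SAP 9.3 governs the abnormality summary, and no text says so.

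**First-dose reactions are found by other routes.** This stands. Clinically significant vital-sign abnormalities are adverse events (Protocol 10.3.1). Anaphylactic and systemic hypersensitivity reactions are events of special interest, notified within 24 hours (Protocol 8.3.6). Addendum #10 identifies them from coded events with blinded medical review, and no step uses the vital-sign baseline. A reader might infer that a reaction would go undetected; it would not.

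**No rate can be attached.** This also stands. Each affected participant is worth at most 1/130 = 0.8 percentage points of one arm's PCSA incidence, but the documents give no count of such participants, and not every extra reading would meet a criterion.

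**Conclusion.** The point holds as a minor defect of definition. Three rules for choosing a baseline coexist: last value by the dosing day, earliest record of the date, and last value before randomization. SAP Section 13 neither lists nor reconciles the difference. For an unscheduled Day 1 post-injection reading, 4.4.6 with recorded times and Addendum #7 read literally each lose the abnormality, by different routes. For a Day 1 whose only reading is post-injection, 4.4.6 loses it and #7 offers no remedy.

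The consequence is limited to the descriptive PCSA table and listing and, under 4.4.6, to the affected participant's later changes from baseline. The primary endpoint has its own averaged baseline, so it is unaffected, as are power and alpha. The conclusion assumes that off-schedule Day 1 readings are timed and entered in the database. How often that happens is not known from the documents.

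**What to change.** Add one item to the SAP addendum that:

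1. defines baseline for these parameters as the last valid value before the date and time of the first injection; if the time is missing, the scheduled Visit 2 value is used, and the existing rule for participants randomized but not treated is kept;
2. states that values recorded after the injection on Day 1 are post-baseline and count for PCSA;
3. states that Addendum #7 does not remove same-date values from the PCSA summaries;
4. records the difference from Protocol 9.4.1 as a change to the planned analysis.

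With this wording the assumed Case 1 reading is compared with 124 and the Case 2 reading with 125, and both are counted. The cost is a few sentences and a date-and-time comparison in the programming. Planned data give the same results as before.
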